## 7.3.2 Analysis of secondary endpoints

All secondary endpoints (change of total score of ALSFRS-R, change in SEIQoL, change of sVC) will be analyzed descriptively and for the FAS only. The Wilcoxon rank sum test will be carried out for group comparisons. Replacement of missing values in the secondary endpoints will not be done. Each statistical test will be performed two-sided at a significance level of 5%. All analysis of secondary endpoint will be interpreted purely exploratory and not as proof of efficacy.

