Statistical analysis	
 
Efficacy: The ITT analysis of the primary endpoint will be done in a confirmatory manner. All other analyzes of primary endpoint, all analyzes of the secondary endpoints, and all safety analyzes are exploratory. For confirmatory data analysis, the log-rank test (one-sided) will be performed. Additionally, the difference in the survival rate (18 months survival) between control group and experimental group will be calculated, incl. 97.5% confidence interval.
 
For further analyzes of primary endpoint, Kaplan-Meier-plots and log-rank-tests will be used.
 
Secondary endpoints: The secondary endpoints will be analyzed descriptively. Differences between experimental group and control group will be investigated using the Mann-Whitney-U-test.
 
Safety: Listing of adverse events, performing of chi-square tests to compare frequencies between control group and experimental group.
 

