### Baseline Visit 1 (V1)

Patients eligible for study participation will enter the study site within 4 weeks after the screening visit and will be randomized to one of the treatment arms.

Blood samples for the determination of blood cell count, creatinine, CK, ASAT, ALAT and blood glucose, will be obtained. A blood sample for genetic testing will be collected as outlined in section 6.3.3. if the patient provided consent to this analysis. Body weight, blood pressure and radial pulse will be documented and lung function will be assessed by measuring the patient's vital capacity. In addition ALSFRS-R and SEIQoL will be performed. The patient will receive study medication according to the randomization list and a study participant card (see appendix VIII).

Any changes in the concomitant medication and adverse events before and during visit 1 will be documented.

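### The secondary comparisons of change ignore the measured baseline value and may lose precision: none to about a third of the variance, depending on figures the protocol does not give

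*Protocol*

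**What the plan says.** Section 7.3.2 of the protocol sets the endpoints and the population: "All secondary endpoints (change of total score of ALSFRS-R, change in SEIQoL, change of sVC) will be analyzed descriptively and for the FAS only". It then names the test: "The Wilcoxon rank sum test will be carried out for group comparisons". The synopsis names the equivalent test: "Differences between experimental group and control group will be investigated using the Mann-Whitney-U-test". Neither place mentions a covariate or a stratum. Tests are two-sided at 5%, and on missing data the section says "Replacement of missing values in the secondary endpoints will not be done". It also limits the claim: "All analysis of secondary endpoint will be interpreted purely exploratory and not as proof of efficacy".

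The baseline values are collected. For Baseline Visit 1, Section 5.1 says "In addition ALSFRS-R and SEIQoL will be performed" and, for vital capacity, "lung function will be assessed by measuring the" patient's vital capacity. The trial schedule agrees, and shows vital capacity at screening as well.

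Randomization (Section 3.6.1) is stratified by bulbar or spinal onset and done separately by center. Nothing in it balances the baseline level of the three measures.

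**The concern.** Subtracting the baseline is not the same as adjusting for it. A change score assumes that a patient who starts one unit higher ends one unit higher. Adjustment estimates that slope from the data. Where the slope is not 1, change remains correlated with baseline: negatively if the slope is below 1, positively if it is above. Two things follow. The planned comparison keeps variance that the V1 value would explain. And a chance difference between the arms at V1 shifts the comparison of change.

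The three secondary objectives (function, quality of life, lung function) rest on these comparisons. They could be answered less precisely than the collected data allow. This would be so even with complete data, so it is separate from how deaths and missing values are treated.

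**Working it through.** **Inputs.** The protocol gives no SD, correlation or power for any secondary endpoint, so there is no stated figure to reproduce. Its sample size of 106 per group (Section 7.1) belongs to the log-rank test. Two quantities are assumed: r, the correlation of baseline with follow-up, and k, follow-up SD divided by baseline SD. The slope of follow-up on baseline is b = r·k. For a realistic group size, 125 per arm times the assumed 18-month survival of 70% and 85% (Section 7.1) gives 125 × 0.70 ≈ 87 and 125 × 0.85 ≈ 106.

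**Step 1: variance.** With baseline SD set to 1:

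- change score: Var = 1 + k² − 2rk
- baseline-adjusted: Var = k²(1 − r²)
- ratio = k²(1 − r²) / (1 + k² − 2rk), which is (1 + r)/2 when k = 1

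| r | k | slope r·k | ratio | variance lost by the change score |
|---|---|---|---|---|
| 0.3 | 1 | 0.30 | 0.65 | 35% |
| 0.5 | 1 | 0.50 | 0.75 | 25% |
| 0.7 | 1 | 0.70 | 0.85 | 15% |
| 0.8 | 1 | 0.80 | 0.90 | 10% |
| 0.9 | 1 | 0.90 | 0.95 | 5% |
| 0.5 | 1.25 | 0.63 | 0.893 | 11% |
| 0.8 | 1.25 | 1.00 | 1.000 | 0% |
| 0.6 | 1.5 | 0.90 | 0.993 | 0.7% |
| 0.9 | 1.5 | 1.35 | 0.777 | 22% |
| 0.5 | 2 | 1.00 | 1.000 | 0% |

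Worked example at r = 0.9, k = 1.5: 2.25 × 0.19 / (1 + 2.25 − 2.70) = 0.4275 / 0.55 = 0.777.

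**Step 2: power.** Take an effect that gives the planned comparison 80% power at two-sided 5%. Adjusted power is approximately Φ(2.80/√ratio − 1.96). For k = 1 this gives 93.5%, 89.9%, 86.0%, 84.0% and 82.0% at r = 0.3, 0.5, 0.7, 0.8 and 0.9.

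That formula is for means. Simulation of the rank tests themselves (normal data, 87 vs 106 patients, k = 1) gave the plain Wilcoxon about 80%. The rank analysis of covariance gave about 93%, 88%, 84%, 83% and 81% at the same values of r. Repeat runs of 4,000 agreed to within about one and a half points.

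With slope at or near 1 (simulated with 100 per arm) there was no gain and no loss: 77.5% vs 77.7% at r = 0.6, k = 1.5, and 77.0% vs 77.1% at r = 0.8, k = 1.25. The type I error of both tests was close to 5%.

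**Step 3: chance imbalance.** With 87 and 106 patients, the difference in baseline means has standard error √(1/87 + 1/106) = 0.145 baseline SD. A baseline difference δ shifts mean change by (b − 1)δ. At r = 0.5 and k = 1, a two-standard-error imbalance (δ = 0.29) shifts it by 0.5 × 0.29 = 0.145. The SD of change there is √(2 × 0.5) = 1, so the shift is 0.145 change-score SD. The effect detectable with 80% power is 2.80 × 0.145 = 0.41 SD, so the shift is about a third of it. At slope 1 the shift is zero.

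**The case against.** A reader might infer that every secondary comparison necessarily loses precision. The protocol does not support that. The loss depends on r and k, which it does not give, and vanishes where their product is near 1. Growing spread is plausible here: entry requires vital capacity above 50% of normal and excludes gastrostomy and recent assisted ventilation (Sections 3.7.1 and 3.7.2), which narrows baseline, while the disease then progresses for 18 months. This stands, and it is why the size is given as a range that includes zero. It does not show that all three instruments have a slope near 1, and a slope above 1 brings the loss back.

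A reader might also infer that the planned test is invalid or biased. It is not. Its type I error is nominal, and randomization balances baseline on average; the shift in Step 3 is conditional on the imbalance that happens to occur. A rank test on change is a conventional choice for bounded scales.

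Finally, the analyses are exploratory, and Section 7 lets the SAP modify the plan. This limits the consequence. But the protocol is not silent: it names one specific unadjusted test in two places.

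**Conclusion.** The point holds as a possible loss of efficiency, not as an error. The planned test ignores a baseline value that is already collected. Under assumed values of r and k, the variance lost runs from none (slope 1) to 35% (r = 0.3, equal SDs). In power terms the gain from a rank-adjusted test at equal SDs runs from about 13 points at r = 0.3 to about 1 point at r = 0.9. No material penalty appeared where adjustment does not help.

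No confirmatory conclusion and no sample size claim depends on this. Nor does adjustment address deaths or unreplaced missing values: a month-18 comparison would still be made among patients with a month-18 value.

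**What to change.** In Section 7.3.2 and the synopsis, make the exploratory group comparison baseline-adjusted:

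- For the p-value, use rank analysis of covariance. Regress the ranks of change on the ranks of the V1 value of the same measure, both arms together, and compare the residuals between arms.
- For the estimate, use ANCOVA with the V1 value and the onset stratum as covariates, and report the adjusted difference with its 95% interval. The rank method alone does not give this interval on the scale of the measure.
- Keep the unadjusted Wilcoxon test as a sensitivity analysis.

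The cost is wording in two places and in the SAP; no data, visits or patients are added. Section 7 calls for a protocol amendment only for major changes to the primary endpoint definition or its analysis. The downside is that the ANCOVA estimate models the mean while the p-value rests on ranks, so the two can disagree on skewed or bounded scores. The text should say in advance which is read for what.

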### Telephone contacts (T1 – T4)

At months 1, 3, 9, 15 the patient or its relative will be contacted by telephone to assess the following items:

- ALS FRS-R
- Weight
- Adverse events
- Changes in concomitant therapies
- Compliance to study drug regimen

If a patient misses a visit or telephone contact the subsequent visit or telephone contact will not be brought forward but will be performed on the scheduled day.

If a patient misses more than one visit, the investigator should contact the sponsor in order to determine how to proceed.

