## 7.1 Sample size

The sample size calculation is based on a comparison of two survival curves using the one-sided log-rank test. Following assumptions were made: Type one error 0.025, power 0.80, recruiting time 6 months, length of follow up period 18 months, 18 month survival rate of 70 % in the control group, 18 month survival rate of 85 % in the experimental group. Under the assumption of equal number of patients in each group, this scenario requires 106 patients in each group, i.e.  $2 \times 106 = 212$  patients in whole trial.

A previous study [GERP ALS-Study; pioglitazone in ALS; NCT00690118, clinicaltrials.gov ID] showed a drop-out rate of about 15 %, screening failure was observed in about 10 %. Thus, in total 250 patients have to be allocated (with consideration of a drop-out rate) and a total number of 278 patients have to be assessed for eligibility.

The sample size calculation was performed using SAS® software, version 9.2, procedure power.

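### Protocol 7.3.2 fixes a rank test on change with no replacement and no rule for death, so a late-visit comparison of ALSFRS-R, SEIQoL or sVC is a comparison of survivors

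*Protocol*

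**What the plan says.** Protocol 7.3.2 covers change in ALSFRS-R, SEIQoL and sVC. These "will be analyzed descriptively and for the FAS only". The method is then fixed: "The Wilcoxon rank sum test will be carried out for group comparisons. Replacement of missing values in the secondary endpoints will not be done". The tests are two-sided at 5%, and the section closes with a limit on interpretation: "All analysis of secondary endpoint will be interpreted purely exploratory and not as proof of efficacy". It names no visit for the comparison and does not say how a patient who has died enters it. The only other rule for missing data, in 7.3.1, concerns incomplete dates for the primary endpoint.

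The planned mortality is in 7.1: 18-month survival of 70% on control against "18 month survival rate of 85 % in the experimental group". V5, the last assessment, is also at month 18. ALSFRS-R is taken at V1 to V5 and also by telephone: "At months 1, 3, 9, 15 the patient or its relative will be contacted by telephone". That makes nine time points. From V1 on, sVC and SEIQoL have five.

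**The concern.** A patient who has died has no change score at later visits. With replacement ruled out, that patient has no rank and drops out of the test; carrying an earlier value forward would itself be replacement. The trial is designed to find a difference in mortality. If it succeeds, the two arms at a late visit are survivors selected to different degrees, and randomisation no longer protects the comparison.

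If faster decliners tend to die first, a life-prolonging drug keeps more of them alive to be measured, and its arm looks functionally worse. A true survival gain could then be reported beside an apparent loss of function, or a true functional gain could be diluted. The synopsis lists these as key secondary endpoints, so readers will look at them closely.

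**Working it through.** **1. The plan's own figure.** From 7.1, HR = ln(0.85)/ln(0.70) = 0.456. A Lakatos log-rank calculation (one-sided 0.025, uniform accrual over 6 months, then 18 months of follow-up) gives 106 per group with power 0.802, as stated. Then 212/0.85 = 249.4, i.e. 250, and 250/0.90 = 277.8, i.e. 278. The 70% and 85% are therefore the rates the design rests on.

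**2. Who can be measured at month 18 (125 per arm).**
- Deaths: 125 × 0.30 = 37.5 on control; 125 × 0.15 = 18.75 on rasagiline.
- Alive, hence the upper limit: 87.5 and 106.25.
- If the 15% drop-outs supply no value, and drop-out is independent of death: 87.5 × 0.85 = 74.4 and 106.25 × 0.85 = 90.3.

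**3. Size of the bias.** The protocol gives no link between decline and death, so it is varied: g is the log-hazard of death per SD of faster decline. Death rates are set to 30% and 15%, drop-out is 15% at random, and the drug has no effect on decline (true difference 0). These assumptions are not in the protocol:
- Run A: mean 18-month ALSFRS-R decline 18 points, SD about 10 (between-patient SD 9, noise SD 4), 1500 trials per setting.
- Run B: mean slope -1 point per month, slope SD 0.6, residual SD 2, 500 trials per setting. The slope model is a random intercept and slope model on all nine time points.

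Wrong direction means a two-sided 5% test significantly favouring placebo; nominal 2.5%.

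| g | A: survivor difference | A: wrong direction | B: survivor difference | B: wrong direction | B: slope model difference | B: slope model wrong direction |
|---|---|---|---|---|---|---|
| 0 | 0.0 | 2% | 0.1 | 2% | – | – |
| 0.5 | -0.8 | 9% | -1.0 | 8% | -0.3 | 5% |
| 1.0 | -1.35 | 14% | -1.7 | 15% | -0.8 | 6% |
| 1.5 | -1.6 | 18% | -1.9 | 22% | -1.0 | 8% |

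Run B is somewhat larger because its between-patient SD at month 18 is 0.6 × 18 = 10.8 points, against 9 in A. The Monte Carlo standard error of the 22% is √(0.22 × 0.78/500) = 1.9 percentage points.

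**4. Earlier visits.** In a run with B's assumptions plus a baseline SD of 5, at g = 1, the bias was -0.25 points at month 6, -0.8 at month 12 and -1.6 at month 18.

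**5. A true functional effect (decline slowed by 20%, true difference +3.6 points).** With the survival effect, run A's survivors show +3.6, +2.8, +2.2 and +1.95 points for g = 0, 0.5, 1.0 and 1.5. Power of the month-18 Wilcoxon test falls from 61% to 45%, 35% and 31%. In run B at g = 1, power is 24% for Wilcoxon and 51% for the slope model; without a survival effect it is 55% and 68%.

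**6. Ranking deaths below survivors (run A).** This favours the drug in 28% to 54% of trials with no functional effect at all, and in 87% to 96% with the 20% effect.

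**The case against.** Several points on the other side are sound.

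- **No visit is named.** A reader might infer a single month-18 test on completers that throws away the intermediate data. 7.3.2 does not say that; the test could be run at every visit, and the choice of visit can be left to the SAP. What stands is that any late-visit test is affected.
- **Drop-outs are not all lost.** Sections 3.7.3, 5.1 and 5.3 ask for an early termination visit with the V5 assessments. The 74 and 90 are therefore a lower case, and 87 and 106 the upper. No such visit can supply a value after death.
- **The bias is conditional.** A reader might infer that the comparison is biased against rasagiline outright. That requires both a real survival difference, which is a planning assumption here, and a link between decline and death, which the protocol does not quantify. At g = 0 there is no bias.
- **Lack of adjustment for baseline or onset** might be read as a further error. The endpoint is already change from baseline, randomisation is stratified by onset, and 7.3.3 plans analyses by stratum. That is not a defect.
- **The consequence is limited.** The endpoints are declared exploratory, and section 7 lets the SAP modify these plans.

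The last point lowers the severity but does not remove the problem. The protocol has not left the matter open: it fixes both the test and the absence of replacement, and a biased estimate misleads under any label.

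**Conclusion.** The point holds in a conditional form. The test and the no-replacement rule in 7.3.2 turn a late-visit comparison into one among survivors, with at most about 87 and 106 of 125 patients contributing at month 18 under the planned mortality. If the drug prolongs life and faster decliners die sooner, the month-18 ALSFRS-R comparison is biased against it by about 0 to -1.9 points for g from 0 to 1.5. Wrong-direction significant results then occur in about 2% to 22% of trials. The direction is consistent across the simulations; the size depends on assumed slopes and an assumed link. Nothing was simulated for SEIQoL or sVC. The confirmatory log-rank result and its type I error are unaffected, so this is a moderate point: it should be changed, but it does not threaten the primary conclusion.

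**What to change.** In 7.3.2:

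- **ALSFRS-R, main secondary analysis:** a linear mixed model with random intercept and slope, using all assessments from V1 to V5 and T1 to T4 up to death or drop-out. Onset stratum is a covariate and the treatment-by-time difference is the estimate.
- **sVC and SEIQoL:** the analogous repeated-measures model on V1 to V5. A linear course was not tested for these, so it should not be taken for granted.
- **Support:** a joint rank analysis with deaths ranked below all survivors, ordered by time of death. Label it as a combined measure of survival and function, not as evidence of a functional effect.
- **Sensitivity:** keep the Wilcoxon test, name its visit, and label it as conditional on being alive and assessed.

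The cost is wording in the protocol (including the synopsis) and the SAP before unblinding, plus modest programming. No new data are needed.

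Three downsides should be stated. The slope model assumes roughly linear decline. It reduces the bias without removing it: about -0.3 to -1.0 points remain for g from 0.5 to 1.5. Its advantage in the simulations is also somewhat flattered, because the data were generated with linear slopes and the variance components were treated as known. The joint rank can favour the drug through survival alone.

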## 7.3.3 Analysis of Subgroups

Subgroup analyzes will be performed for the bulbar and spinal stratum.

#### 7.3.4 Interim analyzes

No interim analyzes are planned.

## 7.4 Analysis of adverse events

All summaries and listings of safety data will be performed for the safety population.

Frequencies of patients experiencing at least one adverse event (AE) will be displayed by body system and preferred term according to MedDRA terminology. Detailed information collected for each AE will include: A description of the event, duration, whether the AE was serious, intensity, relationship to trial drug, action taken, clinical outcome. Summary tables will present the number of patients observed with AEs and corresponding percentages. Additional subcategories will be based on event intensity and relationship to trial drug.

A patient listing of all AEs will be prepared.

## 7.5 Analysis of clinical laboratory findings

Listings will be prepared for each laboratory measure and will be structured to permit review of the data per patient as they progress on treatment.

Summary tables will be prepared to examine the changes of laboratory measures over time. Additionally, shift tables will be provided to examine the changes of laboratory data from normal baseline to values outside the corresponding reference range during/after treatment.

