# 1 INTRODUCTION

## 1.1 Scientific background

Amyotrophic lateral sclerosis (ALS) is a severe neurodegenerative disease characterized by progressive degeneration of the anterior horn cells of the spinal cord, their homologues in the brain stem and the upper motor neurons in the primary motor cortex. Clinically, the disease progresses from initial asymmetric weakness, wasting and atrophy to complete loss of spinal and bulbar motor functions. The upper motor neuron component is clinically mirrored by hyperactive tendon jerks, pseudobulbar emotional lability, and less frequently spasticity.

The ALS Research Committee of the World Federation of Neurology has established research diagnostic guidelines, the El Escorial criteria [1, 2] (http://www.wfnals.org). ALS is considered an orphan disease: its incidence is estimated with 1.5 –3 /100000/year and prevalence rates are 3-6/100000 [3]. Treatment of ALS remains unsatisfactory; riluzole, a benzothiazole derivative and glutamate release blocker, has been approved for use in ALS because of its modest effect on survival [4]. The drug is generally well tolerated by the patients although liver toxicity must be controlled (http://www.cochrane.org).

Based on a rare cause of the disease, mutations in the gene for the cytosolic form of the copper/zinc superoxide dismutase (Cu/Zn SOD), a transgenic animal model has been developed. This G93A model of fALS has led to the discovery of several experimental drugs; in particular, a dose-dependent effect of rasagiline on survival (alone and in combination with riluzole) has been demonstrated in a mouse carrying a low copy number of the human disease-causing gene [5].

Rasagiline [N-propargyl-(1R)-aminoindan] is a selective irreversible second-generation monoaminooxidase (MAO)-B inhibitor with symptomatic efficacy in Parkinson's disease (PD) with a favourable tolerability profile [6]. Preclinical studies have demonstrated that rasagiline has neuroprotective effects both in in vitro and in vivo models, suggested to be related to its propargyl moiety rather than MAO inhibition. Structure activity studies have established that N-propargylamine is essential for the neuronal cell survival activity of rasagiline since this moiety itself revealed similar protective effects and mechanisms of actions [5]

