## 3.7.2 Exclusion criteria

Patients presenting with any of the following criteria will not be included in the trial:

- Previous participation in another clinical study within the preceding 12 weeks
- Tracheostomy or assisted ventilation of any type during the preceding three months
- Gastrostomy
- Any medical condition known to have an association with motor neuron dysfunction which might confound or obscure the diagnosis of ALS
- Presence of any concomitant life-threatening disease or impairment likely to interfere with functional assessment
- Patients on sympathomimetic agents. This includes pseudoephedrine, phenylephrine, phenylpropanolamine, and ephedrine.
- Patients on analgesics with serotoninergic properties such as meperidine, tramadol, methadone and propoxyphen.
- Patients on serotonin reuptake inhibitors (SSRIs). This includes fluoxetine or fluvoxamine.
- Patients on serotonin noradrenalin reuptake-inhibitors (SNRIs) and patients on tricyclic and tetracyclic antidepressants
- Patients on dextromethorphan, St. John's wort, cyclobenzaprine or other MAO inhibitors (selective or non-selective)
- Confirmed hepatic insufficiency or abnormal liver function (ASAT and/or ALAT greater than 3 times the upper limit of the normal range)
- Renal insufficiency (serum creatinine more than 2.26 mg/dL)
- Evidence of major psychiatric disorder or clinically evident dementia precluding evaluation of symptoms
- Known hypersensitivity to any component of the study drug
- Liable to be not cooperative or comply with the trial requirements (as assessed by the investigator), or unable to be reached in the case of emergency
- Female with childbearing potential, if no adequate contraceptive measures are used
- Pregnancy or breast-feeding females

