#### 3.7.3 Withdrawal criteria

Patients can withdraw their consent at their own request without given reasons at all times during the trial. This should be without disadvantages for the patient.

Whenever possible, all patients prematurely discontinuing study medication should perform an early termination visit including the same evaluations as scheduled for visit V5. The reason(s) for premature cessation of a patient's participation during the trial, other than death, should be specified on the case report form.

Study treatment may be stopped prematurely if any of the following events occur, according to the judgment of the investigator:

• Significant intolerance of the study medication, or significant clinical or laboratory findings, e.g. increase in ASAT or ALAT >3 times the upper limit of normal

- Significant intercurrent illness or emergency situation requiring cessation of the study
- The patient wishes to terminate his/her participation in the study
- Investigator judgment that it is in the best interest of the patient
- Failure to comply with the investigational procedures
- Pregnancy
- Technical reasons (change of physician, change of address of volunteer/patient)

Patients who have started double-blind treatment will not be replaced.

For any patient prematurely discontinuing the study, the investigator must:

- Recover all the treatment units given to the patients
- In as far as possible, carry out all the examinations and tests planned for the final visit after withdrawal of the patient from the study
- Fill in the corresponding pages of the case report form, specifying the date and reason for premature discontinuation
- When applicable, ask the patient the reason of his/her Informed Consent withdrawal while fully respecting the patient's rights
- Where possible prescribe a visit 2 weeks after withdrawal in order to control and document any change in the patient's clinical status. If a serious adverse event occurs, the Responsible Nominated Safety Contact must be informed according to the procedures described in section 6.2.2.5. "Immediate reporting of SAEs by investigator".
- All ongoing serious adverse events of withdrawn patients have to be followed up until no more signs and symptoms are verifiable or the investigator has assessed its sequelae, even after the end of the trial.

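### The laboratory shift tables in section 7.5 start only from a normal baseline and end at any out-of-range value, so they miss worsening from a raised baseline and do not separate values above 3 × ULN

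*Protocol*

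**What the plan says.** Protocol section 7.5 plans three laboratory outputs. First, "Listings will be prepared for each laboratory measure", arranged so that each patient can be followed through treatment. Second, there are summary tables of change over time. Third, as an addition, "shift tables will be provided to examine the changes of laboratory data from normal baseline to values outside the corresponding reference range", during or after treatment. No shift from an abnormal baseline is described.

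Three other places bear on this:

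- **Entry (3.7.2).** Patients are excluded for "Confirmed hepatic insufficiency or abnormal liver function (ASAT and/or ALAT greater than 3 times the upper limit of the normal range". Values above 1 and up to 3 × ULN are therefore admissible. For the other safety analytes, only creatinine has an entry limit.
- **Withdrawal (3.7.3).** The list is introduced by "Study treatment may be stopped prematurely if any of the following events occur, according to the judgment of the investigator". One item is significant clinical or laboratory findings, with "increase in ASAT or ALAT >3 times the upper limit of normal" as the example.
- **Background therapy (1.1).** Riluzole is called generally well tolerated, with the reservation that "liver toxicity must be controlled". Every patient must be on it at entry.

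A baseline value exists for every analyte, because at V1 "Blood samples for the determination of blood cell count, creatinine, CK, ASAT, ALAT and blood glucose, will be obtained".

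**The concern.** A shift table shows, patient by patient and by arm, who moved into a worse laboratory category. If only patients with a normal baseline have a row, patients who enter with raised enzymes and rise further are not counted in it. They are also the patients who need the smallest rise to pass 3 × ULN. With a single end category, a trivial excursion and a large one fall in the same cell even for patients who started normal.

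Section 2.3 says that tolerability and safety will be assessed by comparing laboratory values across the two groups, and the shift table is the only categorical, patient-level laboratory comparison that the protocol describes. At stake is how informative that one table is for liver enzymes and for any other analyte that is out of range at entry.

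**Working it through.** The protocol states no figure on this point, so there is nothing to reproduce. The check compares the sections and adds one line of arithmetic.

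**Step 1: who has a row.** The starting category in 7.5 is a normal baseline. Section 3.7.2 admits ASAT and ALAT up to 3 × ULN. The admissible range therefore splits in two: up to 1 × ULN (has a row) and above 1 up to 3 × ULN (no row for that analyte). A patient without a row for ALAT can still have one for an analyte that was normal at baseline.

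**Step 2: how far each patient is from 3 × ULN.** From a baseline of b × ULN, the fold rise that must be exceeded is 3 / b.

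| Baseline b (× ULN) | Row in the described table? | Fold rise to be exceeded, 3 / b |
|---|---|---|
| 0.5 | yes | 3 / 0.5 = 6.0 |
| 1.0 | yes | 3 / 1.0 = 3.0 |
| 1.5 | no | 3 / 1.5 = 2.0 |
| 2.0 | no | 3 / 2.0 = 1.5 |
| 3.0 | no | 3 / 3.0 = 1.0, i.e. any rise |

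The patients nearest to the level named in 3.7.2 and 3.7.3 are exactly those without a row.

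**Step 3: what the end category distinguishes.** The described end point is any value outside the reference range. Three illustrative patients show the effect:

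- from normal to 1.1 × ULN: counted as a shift;
- from normal to 6 × ULN: counted as a shift, in the same cell as the first;
- from 2 to 5 × ULN: not in the table.

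**Step 4: other analytes.** Section 3.7.2 sets no limit for CK, glucose or blood counts, so abnormal baselines on these are admissible and also have no row. Section 4.1.3 lists leukopenia as a frequent effect of rasagiline monotherapy; a patient with a low white count at baseline that falls further would not be in the table.

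**Step 5: where these patients do appear.** The listings and summary tables of change in 7.5 are not restricted by baseline. Section 6.2.2.1 makes an abnormal test result an adverse event if it comes with symptoms, needs further testing or intervention, changes dosing or leads to discontinuation or significant other treatment, or is so judged by the investigator or sponsor. Such events enter the tables of section 7.4 whatever the baseline.

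**Step 6: how many patients.** The protocol gives no proportion with raised baseline values, so no count follows from it.

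**The case against.** The strongest reply is that the sentence in 7.5 states what the shift tables are meant to examine and does not set out their rows and columns. A full baseline by post-baseline table would satisfy it, and section 7 leaves detail to a statistical analysis plan that may modify the protocol. This has some force for fine points such as grading, which are often settled in table shells. It does not remove the point: the protocol itself names the starting and end categories, and a programmer who follows the sentence as written would produce the narrow table.

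The second reply is that other outputs cover these patients, and it largely stands. A reader might infer that the between-arm assessment of liver safety leaves out the patients most at risk. The documents do not support that. The listings and summary tables include every baseline, the adverse event tables cover the whole safety population, the Synopsis plans chi-square comparisons of frequencies, and the monitoring board reviews safety data every three months (6.2.2.7 and 10.8). A rise from 2 to 5 × ULN that led to further testing or to stopping treatment would be reported as an adverse event. What these outputs do not provide is a categorical comparison of all laboratory shifts by arm: listings do not compare arms, summaries of change can obscure a few large rises, and the adverse event route depends on the criteria in 6.2.2.1.

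A reader might also take 3 × ULN as a fixed stopping threshold. Section 3.7.3 gives it only as an example, and stopping is at the investigator's judgment. The liver toxicity named in 1.1 belongs to riluzole, which both arms take, and the monotherapy effects listed in 4.1.3 include no hepatic event.

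**Conclusion.** The point holds, at low severity. As worded, section 7.5 gives no row to a patient whose analyte is already out of range at baseline, including patients with ASAT or ALAT above 1 and up to 3 × ULN, and it does not show how many patients in each arm pass 3 × ULN. This rests on reading 7.5 literally and on the entry limit in 3.7.2; it needs no assumption about effect or prevalence.

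The loss is limited to the shift tables. All safety analyses are exploratory according to the Synopsis, and no error rate, sample size or confirmatory conclusion depends on them. A reader might want to attach a number. Assuming that 5% to 30% of the 250 patients have raised enzymes at baseline would give 250 × 0.05 = 12.5 to 250 × 0.30 = 75, roughly 12 to 75 patients. That range is purely an assumption and nothing in the protocol supports it, so it should not be reported as the size of the problem.

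**What to change.** In section 7.5, replace the restriction to a normal baseline and a single out-of-range outcome with shift tables by treatment arm in the safety set. Cross every baseline category (below, within, above range) with the worst post-baseline category. Where an analyte can go out of range in both directions, show the lowest and the highest value separately. For ASAT and ALAT use three categories: up to 1, above 1 to 3, and above 3 × ULN. These bands use only the level that the protocol already names; under 3.7.2 the highest one should be empty, or nearly so, at baseline.

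The cost is one table specification. Laboratory tests are already scheduled at every visit from V0 to V5, so no new data, visits or patients are needed, and no clinical rule, sample size or alpha changes.
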